6.4.1. Solicited local reactions

Definition

Solicited local reactions at the injection site consist of pain, tenderness, erythema/redness or induration/swelling. They are assessed by the subject in a diary and by the investigator at specific time points stated in the protocol.

Local reactions will be graded using criteria based on the guidance given in US Food and Drug Administration (FDA) Guidance for Industry 'Toxicity Grading Scale for Healthy Adult and Adolescent Volunteers Enrolled in Preventive Vaccine Clinical Trials' for 'Local Reaction to Injectable Products'. The grading of local reactions to injectable product is detailed in section 8.2.9 of the protocol. The grades are Grade 0 (Absent), Grade 1 (Mild), Grade 2 (Moderate), Grade 3 (Severe) and Grade 4 (Potentially life threatening).

The solicited local reactions will be evaluated for the following time intervals:

- Prime immunization up to day 7 (inclusive) after prime immunization
- Boost immunization up to day 7 (inclusive) after boost immunization
- Both intervals combined

The intervals will start with the date and time of the immunization.

Clarification: The interval 'prime immunization up to day 7 after prime immunization' includes study day 1 to study day 8. This applies to the other intervals accordingly.

Analysis

Local reactions with missing time and occurring on the day of prime immunization will be assigned to all intervals starting with the prime immunization. Local reactions with missing time and occurring on the day of the boost immunization will be assigned to all intervals including the boost immunization. Local reactions with missing date will be assigned to each of the respective intervals if it cannot be ruled out, that it belongs to the time interval.

The following analyses will be done for local reactions assessed by the subject, for local reactions assessed by the investigator and for both combined:

Differing from protocol section 9.4.2, the number and percentage of subjects reporting at least one local reaction in each time interval will be summarized for any local reaction and by worst grade.

The denominator of the percentages will be the number of subjects with any information on local reactions in the diary available in the respective time interval.

The number and percentage of subjects reporting at least one local reaction will be summarized by local reaction type (pain, tenderness, erythema/redness and induration/swelling) and by worst grade for each time interval. The denominator of the percentages will be the number of subjects with any information on local reactions in the diary available in the respective time interval.

The following analyses will be done for local reactions assessed by subjects:

Statistical Analysis Plan Version: Final 3.0

Time after prime and after boost from

EudraCT No: 2020-003267-26

- · first dose to first local reaction,
- first dose to first local reaction with grade >=3,
- · first local reaction to last local reaction and
- first local reaction with grade >= 3 to last local reaction with grade >= 3

will be summarized descriptively overall and by local reaction term.

The same variables will be described for any reaction (local or systemic).

Moreover, the frequency of subjects with solicited local reactions and any solicited reactions within 7 days after each dose per day and the frequency of subjects with solicited local reactions within 7 days after each dose by term per day will be analyzed.

The compliance with the diary from each immunization up to 7 days after each immunization will be presented. Therefore, a table giving the number and percentage of subjects with any information on local reactions in the diary (overall and by local reaction term) available per day will be given.

The compliance with the diary based on any information on any reaction (local or systemic) will also be given.

All local reactions from the study will be listed. Additionally, all days with information on local reactions in the diary will be listed.

Local reactions assessed by subject will be presented graphically using a bar plot.

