### Clinical Trial Protocol Including Amendments Nos. 01 to 04 BNT162-04

Page 16 of 133 Version: 10.0 Date: 12 MAY 2021

Procedure / Assessment	Visit 0	Visit 1 Pre- dose	Visit 1 Dosing & Post- dose	Visit 2 at 24±2 h	Phone call at 48±2 h	Visit 3	Visit 4 Pre- dose	Visit 4 Dosing & Post- dose	Phone call at 48±2 h	Visit 5 ~7 d from Visit 4	Visit 5a ~14 d from Visit 4	Visit 6 ~21 d from Visit 4	Visit 7 ~28 d from Visit 4 (EoT Visit)	Visit 8 ~63 d from Visit 4 (FU Visit)	Visit 9 ~162 d from Visit 4 (FU Visit)	Visit 10 ~365 d from Visit 4 (FU Visit)
Day h	-30 to 0	1	1	2		8	22	22		29	36	43	50	85	184	387
Collect subject diaries				x	Xi	x	х			х		x	х	x		
Record AEs since last visit		Х		х		х	X			х	X	х	X	Χį	Χj	Xi
Local reaction assessment/ systemic events	65		Хþ	X		х	Х	Хþ		х		х	х			Ü
Concomitant medication q	х	Х		х		X	х			х		X	х	х	X	Х
Subject wel being questioning					Χi				χi							

- a) Brief (symptom-directed) physical examination; no height measurement.
- b) At 1, 3, and 6 h (±15 min) after immunization.
- c) Vital signs: systolic/diastolic blood pressure, pulse rate, respiratory rate, and body temperature; body weight only at Visit 0.
- d) Urine screening for drugs of abuse (amphetamines, benzodiazepines, barbiturates, cocaine, cannabinoids, opiates, methadone, methamphetamines, phencyclidine, tricyclic antidepressants).
- e) Dipstick urine analysis: glucose, bilirubin, ketone, specific gravity, blood, pH, protein, urobilinogen, nitrite, and leukocytes. Microscopic urinalysis: if warranted by dipstick results, urine sediment will be microscopically examined for the presence of red blood cells, white blood cells, casts, crystals, epithelial cells, and bacteria.
- f) Clinical laboratory tests: (Chemistry) alkaline phosphatase, creatinine, ferritin, C-reactive protein, albumin, alanine aminotransferase, amylase, aspartate aminotransferase, gamma glutamyl transpeptidase, total bilirubin, blood urea nitrogen, glucose, lipase, sodium, potassium, calcium; (Hematology) hemoglobin, hematocrit, red blood cell count, white blood cell count and differential (neutrophils, lymphocytes, monocytes, eosinophils, basophils), platelet count. Only in women who are not WOCBP: follicle stimulating hormone (FSH) at Visit 0 to confirm the menopause status.
- g) Viral screening for human immunodeficiency virus (HIV) 1 or 2, Hepatitis B, Hepatitis C.

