6.4. Primary Analyses

Hereinafter, the primary analyses for Part A are described.

The primary endpoints are solicited local reactions at the injection site, solicited systemic reactions and the proportion of subjects with at least 1 unsolicited treatment emergent adverse event (TEAE).

Clarification: Only local and systemic reactions assessed by subject will be analysed as primary endpoint. As additional analyses, the local and systemic reactions assessed by the investigator will also be included in tables displaying "worst possible grade" for data completeness.

All primary analyses will be performed using the SAF and analyses of adverse events will possibly be repeated using the SAFB.

All primary analysis endpoints will be summarized by group (i.e. by cohort) and all cohorts combined (cohort-total).

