6.4.2. Solicited systemic reactions

Definition

Solicited systemic reactions consist of nausea, vomiting, diarrhea, headache, fatigue, myalgia, arthralgia, chills, loss of appetite, malaise, or fever. They are assessed by the subject in a diary and by the investigator at specific time points stated in the protocol.

Solicited systemic reactions will be graded based on the guidance given in US Food and Drug Administration (FDA) Guidance for Industry 'Toxicity Grading Scale for Healthy Adult and Adolescent Volunteers Enrolled in Preventive Vaccine Clinical Trials'. The grades are Grade 0 (Absent), Grade 1 (Mild), Grade 2 (Moderate), Grade 3 (Severe) and Grade 4 (Potentially life threatening). Fever is graded as Mild (38.0-38.4°C), Moderate (38.5-38.9°C), Severe (39.0-40.0°C and Potentially life threatening (>40.0°C).

The solicited systemic reactions will be evaluated for the following time intervals:

- Prime immunization up to day 7 (inclusive) after prime immunization
- Boost immunization up to day 7 (inclusive) after boost immunization
- Both intervals combined

The intervals will start with the date and time of the immunization.

Clarification: The interval 'prime immunization up to day 7 after prime immunization' includes study day 1 to study day 8. This applies to the other intervals accordingly.

Analysis

Solicited systemic reactions will be analyzed in the same way as solicited local reactions (see Section 6.4.1 of the SAP).

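### Investigator-assessed and combined reaction tables are given the diary denominator, so their numerator can include subjects whom the denominator leaves out

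*SAP*

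**What the plan says.** SAP 6.4.1 describes two separate sources for local reactions: "They are assessed by the subject in a diary and by the investigator at specific time points stated in the protocol". One lead-in then opens the percentage tables: "The following analyses will be done for local reactions assessed by the subject, for local reactions assessed by the investigator and for both combined". Under it come the table of any reaction and worst grade and the table by reaction type and worst grade. Each is followed by the same denominator, the "number of subjects with any information on local reactions in the diary available in the respective time interval". Only after both does a new lead-in narrow the scope to subject-assessed reactions, for the timing, per-day and diary-compliance outputs. The diary denominator therefore sits inside the three-source block.

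SAP 6.4.2 extends this by cross-reference: "Solicited systemic reactions will be analyzed in the same way as solicited local reactions".

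Three other places matter:

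- SAP 6.1.1 makes the analysis-set N the default denominator, but only where nothing else is stated. Here something else is stated.
- SAP 6.4 says "All primary analyses will be performed using the SAF", and membership of that set (SAP 5.1) requires one dose, not a diary entry. The same section limits the primary endpoint to subject-assessed reactions and calls the investigator data additional.
- The protocol's Schedule of Activities (Section 1.3) has a row for local reactions and systemic events. It is marked post-dose at Visits 1 and 4 with a footnote reading "At 1, 3, and 6 h (±15 min) after immunization", and also at Visits 2, 3 and 5, among others.

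**The concern.** A percentage is a proportion only if everyone who can be counted in the numerator is also in the denominator. Site staff check for reactions whether or not the subject fills in a diary, so a subject can have an investigator-recorded reaction in an interval and no diary information in it. Nothing in SAP 6.4.1 limits the investigator or combined numerator to subjects with diary information. A programmer must either count that subject over a denominator that excludes them, or drop them. Two programmers could choose differently and both claim to follow the SAP.

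The mismatch also runs the other way. In the investigator table, a subject with diary information but no investigator assessment in the interval stays in the denominator without being able to contribute a reaction.

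What is at stake is the accuracy of supplementary reactogenicity percentages in cohorts of 12, where one subject moves a rate by several points.

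**Working it through.** **The plan's own figure.** The only numerical design statement is the chance of seeing an event of 15% incidence at least once in 12 subjects, given as 85.8% (SAP 4; Protocol 9.2). 1 − 0.85^12 = 0.8578, so it reproduces. The present point does not depend on it.

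**Inputs.**
- Cohort size 12 (SAP 1.2).
- Denominator: subjects with any diary information in the interval (SAP 6.4.1).
- Investigator checks within each interval: at least the post-dose checks at Visits 1 and 4 (Protocol 1.3).
- m = subjects with investigator data but no diary information in the interval. The documents do not give it. I assume m = 0 to 3.
- k = subjects with a recorded reaction.

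**Case 1: all reactors are counted.** With all 12 assessed by the investigator, the matched figure is k/12 and the SAP rule gives k/(12 − m).

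| m | k = 6, SAP rule | k = 6, matched | k = 12, SAP rule | k = 12, matched |
|---|---|---|---|---|
| 0 | 6/12 = 50.0% | 50.0% | 12/12 = 100% | 100% |
| 1 | 6/11 = 54.5% | 50.0% | 12/11 = 109.1% | 100% |
| 2 | 6/10 = 60.0% | 50.0% | 12/10 = 120.0% | 100% |
| 3 | 6/9 = 66.7% | 50.0% | 12/9 = 133.3% | 100% |

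For 6/12 the exact 95% interval is 21.1% to 78.9%; for 6/11 it is 23.4% to 83.3%. When the count exceeds the denominator, no Clopper-Pearson interval exists.

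**Case 2: the one subject without a diary is a reactor and is dropped (m = 1).** That subject leaves both numerator and denominator, so the comparison is k/12 against (k − 1)/11:

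k/12 − (k − 1)/11 = (11k − 12k + 12)/132 = (12 − k)/132.

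| k | matched k/12 | after dropping (k − 1)/11 | fall in points |
|---|---|---|---|
| 1 | 8.3% | 0.0% | 11/132 = 8.3 |
| 3 | 25.0% | 18.2% | 9/132 = 6.8 |
| 6 | 50.0% | 45.5% | 6/132 = 4.5 |
| 12 | 100% | 100% | 0 |

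**Case 3: dilution in the investigator table.** Suppose all 12 have diary information but one has no investigator assessment in the interval, with 6 investigator-recorded reactors. The SAP rule gives 6/12 = 50.0%; the matched figure is 6/11 = 54.5%.

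**A second route into the mismatch.** SAP 6.4.1 assigns an undated reaction to every interval it might belong to. That can include an interval in which the subject has no diary information.

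**The case against.** The strongest reply is that this will seldom happen. The denominator asks for any diary information over study days 1 to 8 or the matching boost interval, so one entry on one day is enough. Diaries are issued and collected repeatedly over that time. The 109% example further needs all 12 subjects to react, including the one with no diary. This stands as a limit on size. It does not remove the defect: the SAP itself plans for missing diaries, since it conditions on diary information and tabulates diary compliance.

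A reader might infer that the primary reactogenicity results are affected. They are not. SAP 6.4 restricts the primary endpoint to subject-assessed reactions, for which the diary denominator is right. Protocol 8.2.9 gives the investigator's local assessments a validating role and bases the reporting of local reactions on the subject.

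A reader might also infer that the investigator-assessed and combined percentages are invalid across the board, or that reactions would vanish unseen. Neither is supported. The percentages go wrong only where a subject lacks one of the sources for a whole interval. SAP 6.4.1 also lists all local reactions and all days with diary information, so a mismatch could be traced. Exact intervals for percentages are optional (SAP 6.1.1), so their failure above 100% is a minor matter.

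Nor does dropping one confirmed reactor always cost about 8 points (1/12). That holds only for a sole reactor, because the dropped subject leaves the denominator too.

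Finally, restricting numerator and denominator alike to subjects with diary data would be coherent. But SAP 6.4 adds the investigator data for completeness, and that restriction would discard the subjects for whom they add most.

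**Conclusion.** The point holds as a defect in a stated rule, not merely as missing detail. One diary-based denominator is applied to three sources and fits only one of them. It affects the additional investigator-assessed and combined tables, for local reactions and, by cross-reference, systemic ones.

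Its size depends on how many subjects lack a source for an entire interval, which the documents do not say. With none, there is no effect. The assumed case of one subject in 12 without a diary moves a 50.0% rate up to 54.5% or down to 45.5%, depending on an unstated numerator rule, and makes a figure above 100% possible. All these tables are descriptive and no hypothesis is tested. This is a low-severity point that deserves correcting because the correction is simple.

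**What to change.** In SAP 6.4.1, in both places where the denominator is stated, give one per source:

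- Subject-assessed tables: subjects with diary information in the interval, as now.
- Investigator-assessed tables: subjects with at least one investigator assessment in the interval.
- Combined tables: subjects with information from either source, with a footnote giving the number without diary information.

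In SAP 6.4.2, refer to information on systemic reactions, since the cross-reference alone leaves the wording about local reactions in force. SAP 6.5.3 already takes this approach for seroconversion, where the denominator is subjects with data at the visit.

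The cost is a few words and a small programming change, with no new data and no change to the primary analysis. There is one small downside. A subject with only the same-day checks and no diary would count as observed for the full 7 days in the combined table, which can slightly lower that rate. Visit 3 (Day 8 ± 1) and Visit 5 (Day 29 ± 3) can fall outside the interval, so such subjects are possible. The footnote makes their number visible.

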5.1. Analysis Sets

Screened Set (SCR)

The screened set is defined as all subjects who signed informed consent.

Safety Set (SAF)

The safety set is defined as all subjects who received at least one dose of Investigational Medicinal Product (IMP).

Safety Boost Set (SAFB)

The safety boost set is defined as all subjects who received two doses of IMP (prime and boost immunization).

Immunogenicity set (IMM)

The immunogenicity set is defined as all subjects who received at least one dose of IMP and have at least one post-baseline functional antibody titer immunogenicity assessment.

Immunogenicity per-protocol set (IMMPP)

The immunogenicity per-protocol set is defined as all subjects included in the immunogenicity set that have no major protocol deviations as determined by the clinician.

Note: In all analysis sets, subjects will be assigned to the dose cohort according to the actual dose they received ("as treated").

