6.1.1. Tables and Listings

Tables

In general, data will be summarized by cohort and all cohorts combined (cohort-total). Furthermore, selected cohorts may be combined (e.g. young and older cohorts). The cohorts and cohort-total will be presented in columns.

Descriptive summary tables as well as figures will be based on scheduled visits.

Continuous variables will be summarized by group using the following descriptive statistics: number of subjects with non-missing data (n), mean, standard deviation (SD), median, minimum (min) and maximum (max).

Descriptive statistics of titer and fold increase of titer will additionally include geometric mean and its two-sided 95% confidence interval (CI). The geometric mean titer (GMT) is calculated as the mean of the logarithm of the functional antibody titers, back-transformed into the original scale. Two-sided CIs will be obtained by calculating CIs using t-distribution for the mean of the logarithmically transformed assay results and transforming the limits back to the original scale.

Geometric mean fold rise (GMFR) is calculated as the mean of the difference of logarithmically transformed assay results (post vaccination time point – pre vaccination time point) and back-transformed into the original scale. Two-sided CIs will be obtained by calculating CIs using Student's t-distribution for the mean difference of the logarithmically transformed assay results and transforming the limits back to the original scale.

Categorical variables will be summarized by group presenting absolute and relative frequencies (n and %) of subjects in each category (including the category 'missing' if applicable). Percentages will be calculated based on the number of subjects in the respective analysis set (N) as denominator if not stated differently. Percentages may be presented with exact 95% Clopper-Pearson CIs.

SDs as well as CIs will only be calculated if values of at least 3 subjects are available.

Listings

Important Case Report Form (CRF) data as well as all relevant generated and transformed variables together with the original data items will be listed. Unless otherwise specified, cohort will always be included in listings, and listings will be sorted first by cohort, then by subject

number and finally, if applicable, by visit number and/or a relevant date (e.g. date of onset of Adverse Event (AE)).

Programming

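### Post-boost daily reaction percentages and diary compliance keep never-boosted subjects in the denominator, because SAP 6.4.1 states no base for them

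*SAP*

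**What the plan says.** SAP 6.1.1 gives a general rule: "Percentages will be calculated based on the number of subjects in the respective analysis set (N) as denominator if not stated differently". SAP 6.4 names the set: "All primary analyses will be performed using the SAF and analyses of adverse events will possibly be repeated using the SAFB". SAP 5.1 admits to the Safety Set (SAF) anyone with one or more doses. The Safety Boost Set (SAFB) requires both doses, but SAP 6.4 mentions it only for possible repeats of adverse event analyses.

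SAP 6.4.1 departs from the general rule for the interval tables, that is, any reaction, reaction type and worst grade: "The denominator of the percentages will be the number of subjects with any information on local reactions in the diary available" in the interval concerned.

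A separate block on subject-assessed reactions then follows. It includes the by-day summary ("Moreover, the frequency of subjects with solicited local reactions and any solicited reactions within 7 days after each dose per day") and, for compliance, "a table giving the number and percentage of subjects with any information on local reactions in the diary (overall and by local reaction term) available" for each day. Neither has a denominator. SAP 6.4.2 adds: "Solicited systemic reactions will be analyzed in the same way as solicited local reactions".

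**The concern.** A subject who was not boosted has no boost date. That subject cannot have a post-boost reaction or a post-boost diary day, and so does not belong in the base of either percentage. Under the general rule the subject is nevertheless in it.

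Two things are at stake. The daily course of reactogenicity after the boost, which describes a primary endpoint, is diluted and stands on a different base from the interval tables beside it. Post-boost diary compliance looks worse than it was. The dilution grows with the number of unboosted subjects in a cohort, so it can also distort comparison between dose cohorts. With 12 subjects per cohort, one or two people move a percentage visibly.

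**Working it through.** **The plan's own figure.** The plan gives no number on this point. Its only calculated figure, in SAP 4, is the chance of seeing an event of 15% incidence at least once in 12 subjects: 1 − 0.85^12 = 0.858, as stated. It plays no part below.

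**Step 1: which denominator applies.**
- General rule: N of the analysis set, unless stated differently (SAP 6.1.1).
- Set for solicited reactions: SAF (SAP 6.4), at least one dose (SAP 5.1).
- Exception in SAP 6.4.1: subjects with diary information, for the interval tables only.
- By-day and compliance tables: no exception stated, so N is the SAF.

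Unboosted subjects are foreseen. Protocol 7.1 provides for subjects who do not receive the boost and keeps them in the trial. SAP 6.4.3 has an adverse event interval for them, and SAP 5.2 lists receipt of only one vaccination as a possible major deviation.

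**Step 2: ceiling on post-boost days.** Let N = 12 (cohort size, SAP 1.2) and b = number boosted (assumed). Even if every boosted subject reacts and fills in the diary, the largest percentage possible is b/12.

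| b | Ceiling on SAF | Correct ceiling |
|---|---|---|
| 12 | 12/12 = 100% | 100% |
| 11 | 11/12 = 91.7% | 100% |
| 10 | 10/12 = 83.3% | 100% |
| 9 | 9/12 = 75.0% | 100% |

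**Step 3: effect on a daily reaction percentage.** Assume 10 boosted, complete diaries, and 8 subjects reacting on the same day and no others in the interval.
- Interval table, stated denominator: 8/10 = 80.0%.
- By-day table, default denominator: 8/12 = 66.7%.

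The same people and events give two percentages.

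**Step 4: separating unboosted subjects from blank days.** Assume 10 boosted, 1 of them with no entry on the day, and 6 reactors.

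| Quantity | SAF (12) | Boosted (10) | Entry that day (9) |
|---|---|---|---|
| Reaction frequency | 6/12 = 50.0% | 6/10 = 60.0% | 6/9 = 66.7% |
| Compliance | 9/12 = 75.0% | 9/10 = 90.0% | not applicable |

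The move from 50.0% to 60.0% corrects for subjects who were never boosted. The move from 60.0% to 66.7% depends on how a blank day is handled, which is a separate choice.

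After the prime dose everyone in the SAF has been dosed, so only blank days matter. With 6 reactors and 1, 2 or 3 blank entries, the SAF gives 6/12 = 50.0%, while subjects with an entry give 6/11 = 54.5%, 6/10 = 60.0% or 6/9 = 66.7%.

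**The case against.** The strongest points on the other side, and what stands of each:

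- **Blank days are not called reaction-free.** A reader might infer that the SAP counts absent entries as no reaction. It does not. SAP 6.1.3 keeps missing data as missing, and SAP 6.1.1 allows a missing category. This stands. Such subjects do remain in the per-day base, so the percentage still falls.
- **A blank day is properly non-compliant.** A reader might infer that counting a dosed subject's blank day against compliance is an error. It is what a compliance table measures. This stands. Only never-boosted subjects on post-boost days are wrongly counted.
- **An entry-only base is one choice among several.** The documents do not say whether a blank day means missing or nothing to report. If subjects stop writing once symptoms end, an entry-only base overstates late-day frequency. This stands, and it is why Step 4 separates the two moves.
- **Frequency might mean counts only.** This is possible, but SAP 6.1.1 summarizes categorical data as counts and percentages, and the compliance table is explicitly a percentage.
- **The damage is recoverable.** The compliance table gives the daily number with diary information, and SAP 6.4.1 lists all reactions and diary days, so a reader could rebase. The trial is also descriptive, with no formal testing. This limits the consequence but does not make the printed percentage right.
- **No final counts support a size.** This is true. If everyone was boosted and every diary completed, the denominators agree.

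**Conclusion.** The point holds for unboosted subjects on post-boost days. The rule as written leaves them in the base of the by-day reaction percentages and of diary compliance, for local and systemic reactions alike. It is a stated default that produces a diluted figure, and not only a missing detail. SAP 6.4.1 replaces the default for the interval tables, and SAP 6.5.3 does so for seroconversion, so its absence here looks like an oversight.

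The shown percentage is the percentage among boosted subjects multiplied by b/12. With an assumed 10 of 12 boosted, the ceiling is 83.3% and 80.0% becomes 66.7%. These sizes rest on assumed counts of boosted subjects, reactors and entries.

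A reader might go further and conclude that the main reactogenicity results are understated. The documents do not support that: the interval and worst-grade tables have their own denominator and are not affected.

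**What to change.** Add to SAP 6.4.1, and state that it also applies to SAP 6.4.2:

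- Diary compliance: the denominator on each day is the number of subjects who received the respective immunization (the SAFB for post-boost days).
- Per-day reaction percentages: subjects who did not receive the respective immunization are excluded. The denominator is the number of the remaining subjects with diary information in the interval, as in the interval tables. The number with an entry on that day is shown alongside.

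Showing the daily count lets a reader see how much blank days matter without the SAP having to decide what a blank day means. The cost is two or three sentences in the SAP and a changed denominator in the table programs. No new data are needed and no endpoint changes.
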